## Study Design Schematic

**Table 1.** Schedule of study procedures.

Construct	Measure	Initial SMA	3mo SMA	6mo SMA	9mo SMA	12mo SMA	15mo	18mo
14-Day CGM Markers of Glycemic Control	Mean CGM Glucose	X	X	X	X	X	X	X
	Coefficient of Variation	X	X	X	X	X	X	X
	Glycemic Mgmt Indicator (GMI)	X	X	X	X	X	X	X
	CGM Wear Time	X	X	X	X	X	X	X
	CGM TIR	X	X	X	X	X	X	X
	CGM TBR	X	X	X	X	X	X	X
	CGM TAR	X	X	X	X	X	X	X
A1c		X	X	X	X	X	X	X
Youth Surveys	T1DAL	X	X	X	X	X	X	X
	DSMP	X	X	X	X	X	X	X
	SEDS	X	X	X	X	X	X	X
	PAID	X	X	X	X	X	X	X
	CGM Ben & Bur	X	X	X	X	X	X	X
	SMA Evaluation	X	X	X	X	X	X	X
Parent Surveys	P-T1DAL	X	X	X	X	X	X	X
	P-DSMP	X	X	X	X	X	X	X
	P-SEDS	X	X	X	X	X	X	X
	P-PAID	X	X	X	X	X	X	X
	CGM Ben & Bur	X	X	X	X	X	X	X
	SMA Evaluation	X	X	X	X	X	X	X
Semi-Structured Dyad Interview						X		

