## **2.2 Scientific Rationale**

The primary aim of this pilot study is to assess the impact of a 12-month SMA model employing interprofessional facilitator-mediated discussion to promote the uptake and

sustained use of CGM, while also providing peer support, and fostering community in order to improve glycemic control and promote health equity among youth with T1D. Although SMAs have been used in T1D, few have been designed specifically to improve health equity by addressing the needs of diverse youth and their families. This proposed intervention will be developed to meet the needs of non-Hispanic Black and Latinx youth with public insurance. Furthermore, this SMA will be the first specifically developed to support uptake and sustained use of diabetes technology among youth who have been historically least likely to access these technologies.

We expect that the SMA model will lead to high rates of SMA retention and satisfaction, greater CGM wear time and sustained use, improved glycemic control, and improved diabetes specific quality of life, self-management behaviors, and self-efficacy scores compared to patients in the traditional individual appointment model. The interprofessional model incorporating CDCES, psychology, and nutrition will allow for youth and caregivers to interact with the entire diabetes care team and will also allow for sufficient time to focus on both education and strategies to cope with the psychosocial burdens and challenges needed to optimize adherence and outcomes. Lessons learned from this comprehensive interprofessional SMA will also provide insights that will allow for development of additional strategies needed to promote equal opportunity for all youth to achieve health and quality of life targets without being hindered by race, ethnicity, or socioeconomic status.

We propose to recruit up to 20 underserved children with poorly controlled T1D and their primary diabetes caregiver. Inclusion criteria are: ages 8-12, T1D duration of at least 1 year, at least one A1c value  $\geq 9\%$  in the past year, Black race and/or Latinx ethnicity, public health insurance, and English fluency in the youth and parent. For the purposes of this study, because non-Hispanic black and Latinx youth with public healthcare insurance are the least likely to have access to CGM technology, we will use the term underserved to specifically refer to this population.

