## **Section 4: Study Design**

Dyads of youth with T1D aged 8-12 years and their primary diabetes caretakers identifying as non-Hispanic Black or Latinx will be recruited to participate in a prospective cohort pilot study exploring feasibility and acceptability of SMA and the impact on glycemic control, self-management skills, and health related quality of life. This trial will employ an enrollment visit, SMA visits every 3 months over a 12-month study period, and a follow-up 6-month observational period to continue to evaluate outcomes once patients return to routine individual follow up care. The study will include a single intervention group participating in the SMA visits (n=20).

All staff participating in the SMA visit will receive comprehensive training on how to facilitate the SMA discussion sessions effectively. All topics that will be covered at each SMA visit will be reviewed by the study staff ahead of the visit. Potential participants will

be screened for participation using our electronic medical records system and will be approached during routine clinical visits. After explaining all study procedures, informed consent using an IRB-approved consent form will be obtained for all participants. After obtaining consent, a blinded Dexcom G6 CGM will be placed on the participant. Participants will be instructed to wear the blinded CGM for 10 days in order to obtain baseline glycemic control data prior to starting the SMA visit intervention. At the completion of the 10 day wear period, participants will mail back the blinded CGM in a pre-addressed envelope so that the data can be assessed within 30 days of the wear time. Because SMA visits will be used in place of routine clinic visits and because participants will not require any additional in person study visits, we anticipate significant interest in participation with minimal barriers. Secure REDCap surveys will be sent to participants via email 1 week before each follow-up visit. If the surveys have not been completed at the time of the visit the participant will be asked to complete the measures using an iPad or paper in clinic at the time of their visit. Youth who elected not to use a CGM for routine clinical care, will be asked to wear a blinded professional CGM for 10 days prior to each visit whenever possible.

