**Initial SMA:** The structure of the group visits will be reviewed with patients and families, and all members of the diabetes team will introduce themselves and explain their role in diabetes care. As some patients will be CGM naïve before this visit, education will focus on insertion and removal of the CGM along with appropriate use of the CGM receiver, alerts and alarms, data sharing, and troubleshooting common CGM problems. Established sharing of CGM data between patients and the diabetes clinical care team will be confirmed before the end of the visit. The group visit will conclude with a review of the core concepts discussed, and patients will set goals for the next SMA.

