#### Follow up SMA at 3, 6, 9, and 12-months

Follow up SMA will be scheduled 3, 6, 9 and, 12 months from the initial group visit. Data will be collected from routine clinical care, including height, weight, BMI, and a point of care fingerstick A1c. Survey measures will be completed again as described previously. CGM data will be analyzed for the 14 days preceding each visit. Chart review from the time of the initial baseline visit will be conducted to assess the incidence of DKA, severe hypoglycemia, ED visits, and hospital admissions. Details obtained from the chart review will be confirmed with participants. Data from the CGM will be obtained through online software used to securely query these devices for routine clinical care (Dexcom Clarity).

Discussions and education guided by the facilitators will focus on issues that have been described in the literature as potential barriers to CGM use and adherence. Recurrent alerts and alarms can result in alarm fatigue, and falsely low glucose readings and sensor or transmitter failures have been cited as reasons for discontinuing CGM use. The continuous nature of CGM data has been shown to place significant demands on patients and their families, and to create stress related to the constant need for

diabetes-related attention. Follow up visits will focus on optimized use of CGM alarms and prevention of alarm fatigue. Psychologists and CDCES will discuss strategies to cope with the on-body presence and potential embarrassment resulting from CGM wear and to optimize parent-child communication surrounding CGM. Nutritionists will highlight the impact of different foods on glycemic trends and discuss strategies to optimize control. SMA will also allow ample opportunity to jointly review deidentified CGM reports and how to effectively interpret data and make management changes in response to CGM data, empowering patients and families to improve self-management and reduce stress related to CGM use. Active participation in discussions and group exercises will continue to strengthen the community feeling and social support network within the SMA group. Any participant that chooses to discontinue CGM during the 12 month study period will wear a blinded CGM 10 days prior to the follow up visits to allow for complete data collection.

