### **8.2 Statistical Hypotheses**

Primary Outcome: feasibility and acceptability of SMA among underserved youth with T1D.

Hypothesis 1a. Rates of SMA retention (>80%) at 12-months and satisfaction with visits (>80%) will be high.

Null Hypothesis 1a: n/a

Hypothesis 1b: Thematic analysis of semi-structured interviews will identify high satisfaction with SMA.

Null Hypothesis 1b: n/a

Secondary Outcome: preliminary impact of SMA on glycemic control, self-management skills, self-efficacy, diabetes related quality of life, and treatment satisfaction among underserved children with T1D and their caregivers

Hypothesis 2a: CGM percentage wear time and sustained use, as defined by use within the 2 weeks prior to the visit, will be greater upon completion of the SMA intervention at 12 months compared to baseline

Null Hypothesis 2a: CGM percentage wear time and sustained use, as defined by use within the 2 weeks prior to the visit, will not be significantly different upon completion of the SMA intervention at 12 months

Hypothesis 2b: CGM time in range (70-180 mg/dL) will be greater and the glucose management indicator (GMI) lower for youth upon completion of the SMA intervention group at 12 months compared to baseline.

Null Hypothesis 2b: CGM time in range (70-180 mg/dL) will not be significantly different upon completion of the SMA intervention at 12 months

Hypothesis 2c: Diabetes-specific quality of life, self-management behaviors, and self-efficacy scores will be greater upon completion of the SMA intervention at 12 months compared to baseline.

Null Hypothesis 2c: Diabetes-specific quality of life, self-management behaviors, and self-efficacy scores will not be significantly different upon completion of the SMA intervention at 12 month

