### **Analysis of the Secondary Efficacy Endpoint(s)**

Glycemic variability indicators will be obtained from CGM downloads for the 14 days prior to a follow-up data collection time point. As guided by published standardized CGM metrics, data will be transformed to identify number of measurements and percent TIR, time below range (<70 mg/dL) (TBR), and time above range ( $\geq 180$  mg/dL) (TAR), mean sensor glucose, and coefficient of variation (CV) of glucose values during each 14-day period. We also will track the percent CGM wear time.

CGM data will be analyzed using library GLU in R. using mixed effect models. These models will quantify the impact of our intervention on glucose control over time. The independent variables will be baseline time in range, child age, and a random subject effect to account for correlation of measurements on the same subject. Interaction terms of age and baseline time in range with the intervention will explore possible effect modification ( $p < 0.10$ ) of these characteristics. We will also explore differences between time points and average outcome by parent education level and income. Results will be reported as least-squares means (LSMEANS) with standard errors. Casewise deletion will be used to handle missing data.

A battery of validated survey measures exploring diabetes-specific self-management skills and quality of life will be completed by the child and caretaker, including: Type 1 Diabetes and Life (T1DAL), Diabetes Self- Management Profile (DSMP), Self-Efficacy for Diabetes (SEDS), and Problem Areas in Diabetes (C-PAID). Perceived benefits and barriers to CGM use will be assessed using the CGM Benefits and Burdens scale. Surveys will be completed by a single, consistent parent/caregiver throughout the study, preferably the one most involved in medical care. We will summarize self-management skills and treatment satisfaction by different time points. Differences in participant self-management skills and patient satisfaction will be reported as mean Likert scale score and standard deviation. Similar analysis using linear longitudinal regression analysis will be conducted. Results will be reported as least-squares means (LSMEANS) with

standard errors. Casewise deletion will be used to handle missing data.

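### Sustained CGM use is judged only from the two weeks before each visit, so it cannot separate continuous wear from wear around visits, and study-requested blinded wear is not excluded

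*Combined protocol and SAP*

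**What the plan says.** Section 2.2 makes persistence a purpose of the trial: "this SMA will be the first specifically developed to support uptake and sustained use of diabetes technology".

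Hypothesis 2a in Section 8.2 is about "CGM percentage wear time and sustained use, as defined by use within the 2 weeks prior to the visit" and predicts that these "will be greater upon completion of the SMA intervention at 12 months compared to baseline". It sets no minimum amount of use and no requirement for the time between visits.

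The same window recurs elsewhere:

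- Table 1 puts CGM wear time in the block headed "14-Day CGM Markers of Glycemic Control".
- Section 6.3 states: "CGM data will be analyzed for the 14 days preceding each visit". Section 6.4 repeats the 14-day query of Dexcom Clarity.
- Section 8.4 states: "Glycemic variability indicators will be obtained from CGM downloads for the 14 days prior to a follow-up data collection time point". It then says that percent wear will be tracked, and gives no other window.

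Table 2, the analytical plan for feasibility and acceptability, lists the percentage continuing on CGM at all assessment time points without defining it. Section 8.1 says there will be no formal SAP, so no other document supplies a definition. Nothing in the protocol plans to use wear data from between the windows.

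Two further provisions matter. Sections 4 and 6.3 ask children who stop CGM to wear a blinded sensor for the 10 days before visits, and Section 4 asks the same of those who chose not to use one. Section 5.2 admits only children without CGM use in the 60 days before enrolment, and baseline data come from a 10-day blinded sensor (Section 4).

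**The concern.** Persistence over a year is a property of the whole interval between visits, but the stated rule looks only at its last two weeks. Children with very different patterns, such as daily wear all year and wear confined to the fortnight before each appointment, receive the same classification and the same wear percentage.

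The blinded sensor adds a second problem. It is there to keep glucose data complete in children who are not using CGM, yet it is worn inside the window that defines use. The plan does not say that only the child's own CGM counts, so a child who has stopped could be recorded as a sustained user.

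At stake is the sustained-use result under Hypothesis 2a and, if the same rule is carried over, the continuation percentage in Table 2. Section 2.4 expects the results to inform later randomized studies, which would inherit any misstatement of persistence.

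**Working it through.** The plan gives no numerical target, power or error rate for sustained use, so there is no figure of its own to reproduce. The check is of what the rule can see.

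**Inputs.** The window is 14 days (Sections 6.3, 6.4, 8.2; Table 1). Follow-up SMAs are at months 3, 6, 9 and 12, with assessments 3 and 6 months after the last SMA (Section 6.3). Blinded wear is 10 days before visits (Sections 4, 6.3). One quarter is taken as 365/4 = 91.25 days.

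**Coverage.**

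- Intervention year: 4 × 14 = 56 days; 56/365 = 15.3% observed, 84.7% not observed.
- All 18 months: 6 × 14 = 84 days; 84/547.5 = 15.3%.
- The 12-month comparison in Hypothesis 2a: 14/365 = 3.8% of the year.

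**Wear in the window against wear over the quarter**, for a child who wears a sensor only on the last d days before each visit (window = d/14, quarter = d/91.25):

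| d | Window | Quarter |
|---|---|---|
| 14 | 100% | 15.3% |
| 10 | 71.4% | 11.0% |
| 1 | 7.1% | 1.1% |

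Read literally, even d = 1 is use within the two weeks.

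**Blinded wear.** A child who has stopped personal CGM but wears the blinded sensor as asked has 10/14 = 71.4% wear in the window. If the child stopped before the interval began, personal wear over that interval is 0%.

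**Baseline.** Entry requires no CGM use in the preceding 60 days, so personal use at entry is zero by design, and almost any personal use at month 12 exceeds it. If the baseline blinded sensor is counted instead, full compliance gives 10/10 = 100% of the days requested, or 10/14 = 71.4% of a 14-day window. Neither is a measure of the child's own prior use.

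**Illustration (assumed mix, not in the documents).** Of 20 children, 12 wear CGM continuously, v wear it only in the 14-day windows, and the rest do not wear it.

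- v = 2: the rule gives (12 + 2)/20 = 70% sustained users.
- v = 4: 16/20 = 80%.
- v = 6: 18/20 = 90%.

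In all three cases the proportion wearing CGM continuously is 12/20 = 60%. With v = 4, mean wear is 80% in the window and (12 × 100% + 4 × 15.3%)/20 = 63.1% over the quarter.

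**The case against.** A reader might infer that the window is systematically inflated because families are prompted just before visits. The documents do not support that. The reminders in Section 5.6 concern SMA attendance, not sensors, and their timing is not stated. The one dated contact is about questionnaires: "Secure REDCap surveys will be sent to participants via email 1 week before each follow-up visit". It falls inside the window but says nothing about wear. Section 4 has the endocrinologist review the 14 days before the visit, but does not say that families are told which days are reviewed. Data sharing with the care team is also in place from the start, which weakens the idea that only pre-visit wear is visible. Upward bias from visit-driven wear is therefore possible, not shown.

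Other points on the plan's side:

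- The 14-day window follows published CGM metrics, and one consistent window is a reasonable choice for a pilot. That stands for the glucose measures. The protocol gives no reason why it should represent persistence over a year.
- Sustained use is paired with percentage wear, so sparse use inside the window would show. That is true, but full wear confined to the window would not.
- The wear sentence in Section 8.4 has no window of its own, the Table 2 measure is undefined, and stopping CGM is recognised as an event. These points stand: the 14-day reading of wear rests on Table 1 and Hypothesis 2a, and extending it to Table 2 is an inference. They argue for a definition, since none is given.
- Hypothesis 2a is a secondary hypothesis, compared at month 12 only, in a single-arm pilot of up to 20 dyads. The primary CGM benchmark is initiation. This limits the weight of the point but does not remove it.

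**Conclusion.** The point holds as a limit of the definition. As written, the rule observes 15.3% of the intervention year, and 3.8% for the 12-month comparison. It cannot tell continuous use from use around visits, and it does not exclude blinded study wear that could give a child who has stopped a wear figure of 71%. These conclusions follow from the wording and simple arithmetic, and need no assumption about behaviour.

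The effect on the reported result is unknown, because the documents do not say how many children would wear sensors only before visits or how blinded wear would be coded. The 70% to 90% against 60% in the illustration shows what an assumed mix would do and is not a forecast. The change is a low-cost improvement to a secondary measure that bears on a stated purpose of the trial.

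**What to change.** In Sections 8.2 (Hypothesis 2a), 6.4 and 8.4:

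1. Compute personal-CGM wear from Clarity over the whole interval since the previous visit, and exclude blinded study sensors.
2. Define sustained use as wear at or above a percentage that the study team sets in advance, applied to each interval through month 12. Report the date of last personal use for children who stop.
3. Use the same definition for the continuation percentage in Table 2.
4. Keep the 14-day window for TIR, TBR, TAR, mean glucose, CV and GMI.
5. Report sustained use as a proportion with a confidence interval, and wear by interval, in place of a test against baseline, which has no like-for-like value.

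The cost is protocol wording and a longer date range in a query already made at each visit, with no added visits or devices. The reported wear may be less favourable. The change assumes that Clarity holds the full between-visit record. Section 4 supports access ("Established sharing of CGM data between patients and the diabetes clinical care team will be confirmed before the end of the visit") but does not say how much history is kept. If the record is incomplete, report the coverage obtained and limit the claim to use in the two weeks before visits.

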### **8.3 Analysis Datasets**

Data analysis will be conducted according to a per-protocol analysis as we will be unable to obtain appropriate data from those who withdraw from the study. Participants with incomplete data will be included in analyses when possible.

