SMA Structure: SMAs will consist of 4-6 underserved youth with T1D and their primary diabetes caregiver. All youth and caretakers will complete standard check-in procedures with the clinic medical staff, including routine clinical intake questionnaires, vital sign assessments and point-of-care fingerstick A1c measurements. Before each session, dyads will be invited to submit questions to the research team that will then be anonymously reviewed and discussed among the group during the SMA. In the event that no questions are submitted by families, the facilitator will begin the discussion with stories and questions related to technology use and potential barriers in order to focus the discussion on the aspect of diabetes management being highlighted in that specific SMA. After discussing the questions, the facilitator will lead a group discussion focusing on the topic of the day. During each visit, the facilitator role will be shared by a pediatric endocrinologist, CDCES, nutritionist, and psychologist. Youth and caregivers will individually meet with the endocrinologist at different time points during the session to update personal management plans and goals of care. The group visit will conclude with a review of the core concepts discussed. Youth will be encouraged to set and share individual goals to be addressed before the next SMA.

Enrollment visit: This visit will occur at a routine clinic visit once a patient expresses interest in participating in the study. Alternatively, patients expressing interest in enrolling who are unable to do so at a routine clinic visit will have the option to come back for enrollment at a different time. A study team member will meet with the patient and family to review the study details and obtain consent. Randomization will be completed after consent has been obtained. A blinded Dexcom G6 pro CGM will be placed on the patient and be worn for 10 days in order to collect baseline data prior to starting the intervention. Phone applications that will allow for sharing of CGM data between patients and the diabetes clinical care team will be downloaded and established before the end of the visit.

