### **5.7 End of Participation Criteria and Procedures**

Participants are free to withdraw from participation in the study at any time upon request. The reason for participant discontinuation or withdrawal from the study will be recorded on the Premature Termination Case Report Form (CRF). Subjects who sign the informed consent but do not receive the study intervention may be replaced. Subjects who sign the informed consent form, begin the study intervention, and subsequently withdraw, or are withdrawn or discontinued from the study, will try and be replaced.

Participants who experience significant psychological distress as a result of the intervention or whose presence at SMA visits will be terminated from study participation. Anyone experiencing psychological distress will be referred to the diabetes psychology team for support (Drs. [name] and [name], Co-I's).

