#### **Analysis of the Primary Efficacy Endpoint(s)**

We will track recruitment, enrollment, participation, and retention through a CONSORT table (Table 2) for the intervention group. Feasibility benchmarks include: recruitment (>60% of reached/eligible participants), CGM initiation, (>80%), SMA sessions attended (>80%), and retention (>80%). In addition, feasibility encompasses demographic characteristics of the enrolled sample, with enrollment and overall increased uptake of CGM among youth from historically underrepresented racial and ethnic backgrounds

(Black race and/or Latinx ethnicity) and income levels. Attrition data and team feedback will help determine how recruitment rates may be improved. Acceptability will be assessed using satisfaction surveys and determined by a high level of satisfaction with participation, perceived utility of the intervention content, and perceived benefit from participation (>80% reporting that they were satisfied and perceived utility and benefit). We will report summary statistics on each feasibility and acceptability item in the questionnaires (mean and standard deviation well as percent answering a specific Likert level). Acceptability also will be examined by key demographic characteristics, including participant age and race/ethnicity.

Parent-child dyads will participate in semi-structured interviews to assess satisfaction with the SMA. Thematic analysis of qualitative data will be conducted by two team members who will independently review interview transcripts to generate initial codes. Initial codes will be discussed by the group to generate a list of second-cycle codes and each team member will then apply the coding framework to all transcripts before identifying dominant themes. ATLAS.ti software will be used to organize and analyze the qualitative data.

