## **8.5 Sample Size**

As this is a pilot study, we plan to enroll up to 20 parent-child dyads. We anticipate low dropout rates, but do plan to enroll new subjects to keep the total number of subjects at up to 20 in case of attrition. If there is a sufficient number of new subjects enrolled to replace those that drop out, a new SMA group will be created so that newly enrolled subjects will be able to start the intervention from the baseline visit.

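### Section 8.3 sets a per-protocol analysis without exempting the primary outcome, and four >80% benchmarks name no denominator although leavers are replaced

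*Combined protocol and SAP*

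**What the plan says.** Section 8.3 sets one analysis set for the whole study: "Data analysis will be conducted according to a per-protocol analysis as we will be unable to obtain appropriate data from those who withdraw". The next sentence keeps participants with incomplete data where possible. The per-protocol set is not defined further, and Section 8.1 says that there will be no formal SAP.

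The primary outcome is feasibility and acceptability. Section 8.4 lists the feasibility benchmarks as "recruitment (>60% of reached/eligible participants), CGM initiation, (>80%), SMA sessions attended (>80%), and retention (>80"%). Only recruitment carries a denominator. Acceptability is ">80% reporting that they were satisfied and perceived utility and benefit"; Section 6.4 adds a Likert score of 4 or 5, which fixes the numerator but not the denominator. Table 2 repeats the percentages without saying of whom.

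Leavers are replaced. Section 5.7 covers those lost before the intervention ("Subjects who sign the informed consent but do not receive the study intervention may be replaced") and those who "begin the study intervention, and subsequently withdraw, or are withdrawn or discontinued from the study, will try and be replaced". Section 8.5 says the investigators "do plan to enroll new subjects to keep the total number of subjects at up to 20 in case of attrition". No section says how a leaver or a replacement counts towards any benchmark.

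**The concern.** Leaving the study is part of what feasibility measures, so a set that drops leavers can remove unfavourable results from the primary outcome. The reason given in Section 8.3, that usable data cannot be obtained after withdrawal, does not fit these measures. Withdrawal is itself the retention result. Sessions attended and CGM started before leaving are known from study records. Section 6.3 also asks those who withdraw to come to an end-of-study visit, so some data from them are expected.

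Replacement adds a second ambiguity: the denominator could be filled places, the first 20 dyads, or everyone who ever consented. With about 20 dyads and a strict cut-off, that choice can decide whether a benchmark is met. Section 2.4 expects the results to inform later randomised studies, and no later analysis document is planned to settle the question.

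**Working it through.** **Inputs from the documents.** Up to 20 dyads (Section 8.5); a strict >80% rule (Section 8.4); 5 SMA sessions, at the initial visit and months 3, 6, 9 and 12 (Section 4, Table 1); enrolment counted at signed consent (Section 6.2). Section 8.5 expects low dropout but gives no rate, so the leaver counts and behaviours below are assumptions. The plan offers no calculation of its own to reproduce. On 20 dyads, >80% requires at least 17 (17/20 = 85.0%), because 16/20 = 80.0% does not exceed 80%.

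**Attendance.** Assume that stayers attend 90% (4.5 of 5 sessions) and that 4 leavers attend *a* of 5. Completers alone give 90%.
- All consented, no replacement: (16 × 4.5 + 4*a*)/100 = 76.0%, 80.0%, 84.0% for *a* = 1, 2, 3. The first two miss the benchmark.
- All consented, all 4 replaced by dyads who also attend 90%: (20 × 4.5 + 4*a*)/120 = 78.3%, 81.7%, 85.0%. Only the first misses.

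**Acceptability.** Assume no replacement, and that each leaver attended at least one SMA.
- One leaver, not satisfied; 16 of 19 completers satisfied: 16/19 = 84.2% (met) becomes 16/20 = 80.0% (missed).
- Four leavers, none satisfied: completers meet the benchmark from 13/16 = 81.3% upwards, but even 16/16 becomes 16/20 = 80.0% (missed).
- If every leaver is satisfied, the two denominators give the same verdict in these cases.

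**CGM initiation.** Assume that 18 of 20 starters initiate, and that dyads who consent but never start do not. The figure is 18/20 = 90.0% on starters. With 1, 2 or 3 consent-only dyads replaced and kept in the denominator it is 18/21 = 85.7%, 18/22 = 81.8% or 18/23 = 78.3%. Only the last misses.

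**Retention**, all consented dyads, *k* leavers:

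| *k* | No replacement, (20 − *k*)/20 | All replaced by dyads who stay, 20/(20 + *k*) |
|---|---|---|
| 3 | 85.0% | 87.0% |
| 4 | 80.0% (missed) | 83.3% |
| 5 | 75.0% (missed) | 80.0% (missed) |

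With 4 leavers the first 20 dyads miss the benchmark while the count including replacements meets it. How replacements count therefore matters even when no leaver is dropped. Full replacement is an upper end: with 18 months per subject and a study of 18-24 months (Protocol Summary), a replacement must start by about month 6 (24 − 18) to finish.

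**The case against.** A reader might infer that retention would be 100% by construction, since a per-protocol set contains only those who stayed. The documents do not support that as the likely intention. Section 8.4 tracks enrolment, participation and retention in a CONSORT table and uses attrition data. Table 2 lists the percentage completing follow-up and the percentages with missing data. Those measures make sense only if leavers are counted, and the reason in Section 8.3 concerns measured data rather than a headcount. This stands for retention. It does not settle attendance, CGM initiation or acceptability.

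The verdict changes come from chosen scenarios. With 3 or fewer leavers, retention passes on every denominator. The one-leaver acceptability case needs exactly 16 of 19 completers satisfied: 17/19 becomes 17/20 = 85.0% and still passes, and 15/19 = 78.9% fails already. After the intervention has begun, replacement is conditional: "If there is a sufficient number of new subjects enrolled to replace those that drop out, a new SMA group will be created", while "SMAs will consist of 4-6 underserved youth with T1D and their primary diabetes caregiver". Three or fewer late replacements would not fill such a group. The exact 95% intervals for 16/20 (56.3% to 94.3%) and 20/24 (62.6% to 95.3%) overlap almost entirely. The benchmarks are descriptive, with no null hypothesis (Section 8.2) and no numerical go/no-go rule. All of this stands and limits the size of the problem.

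The individual listings promised in Section 8.4 and the session counts in Table 2 would allow partial recomputation. They cannot recover ratings never collected from leavers.

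Two further readings go too far. Table 2 takes satisfaction after the intervention, while Table 1 schedules an SMA Evaluation at every visit to month 18. That is a conflict only if the two are the same instrument, and the items are not listed. Casewise deletion in Section 8.4 contradicts the inclusion of incomplete data in Section 8.3 only if whole children, rather than missing visits, are deleted.

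**Conclusion.** The concern holds in a bounded form and should be fixed. As written, the per-protocol rule covers the primary outcome, four benchmarks have no denominator, and leavers are replaced. Followed literally, the rule drops leavers from attendance and acceptability and can turn a missed benchmark into a met one: 90% against 76.0% for attendance with 4 unreplaced leavers attending one session each, and 84.2% against 80.0% for acceptability with one dissatisfied leaver. These sizes rest on assumed dropout and behaviour. They show that a verdict can change, not that it will. The documents do not support saying that retention is guaranteed to pass or that leavers are meant to be hidden.

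**What to change.** 1. In Sections 8.3 and 8.4, exempt the primary outcome from the per-protocol set. Base CGM initiation, attendance and 12-month retention on all consented dyads, so that a replaced dyad is never removed from the denominator. Define attendance as sessions attended, including make-up sessions, over all planned SMA sessions.
2. Report the result for the originally enrolled dyads beside the result including replacements, and state in advance which is set against the benchmark. Pooling alone can favour the benchmark (20/24 = 83.3% against 16/20 = 80.0%).
3. For acceptability, include everyone who attended at least one SMA, separately for child and parent. Use the end-of-intervention rating. For leavers, use the last rating made after an attended SMA or at the end-of-study visit. Surveys are emailed a week ahead, so a form completed before the first SMA should not count. Report non-response and a completers-only figure.
4. Analyse the longitudinal secondary outcomes on all observed visits of all enrolled children. This changes little if deletion was meant visit by visit.
5. As a side clarification, reconcile replacement with the accrual ceiling of 20 dyads, since enrolment is counted at consent.

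The cost is mostly wording in Sections 5.7, 8.3, 8.4 and 8.5 and Tables 1 and 2. Two points need confirming: that the SMA Evaluation contains the satisfaction, utility and benefit items, and that it is given at the end-of-study visit. The feasibility figures may look slightly less favourable.
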